Cohort 1. For a 1 sample test of proportions our hypothesis is that booster vaccine dosing will induce detectable immunity by the spike IgG assay in at least 20% of individuals. Null hypothesis is a positivity rate of 10% to account for some test variability and therefore the alternative hypothesis is $p > 30\%$. Our planned sample size of up to 250 will have ample power ($>95\%$) to detect such a difference in our primary endpoint and will still retain 80% power and 5% significance in the secondary preplanned subset analyses as long as cohort sizes per subset are >26 . We anticipate the large majority of patients will be hematologic malignancy patients and such preplanned subset analyses will include two cohorts, the highly immune suppressed (prior anti- CD20, CAR-T, or SCT therapy), and all others (solid tumor/hematologic malignancy patients) who do not fall into the first cohort. We anticipate cohort sizes of at least 26 per cohort based on the numbers of seronegative patients identified in our prior study.

Cohort 2. Our null hypothesis is that the additional homologous booster vaccine dosing will induce detectable immunity (positive spike IgG test result higher than the predefined threshold for seropositivity—i.e. >1000 AU/ml) by the spike IgG assay in at least 25% of individuals. Alternate hypothesis is that heterologous vaccination with the AdCov2.S vaccine will increase this seroconversion rate by an additional 25%- that is to 50%. With an alpha of 0.05 and 80% power to detect the difference, we would require a sample size of 46 in each group. Accounting for 5% dropout rate, we will thus use a planned sample size of up to 100 subjects. We anticipate the large majority of patients will be hematologic malignancy patients and such preplanned subset analyses will include two cohorts, the highly immune suppressed (prior anti-CD20, CAR-T, or SCT therapy), and all others (solid tumor/hematologic malignancy patients) who do not fall into the first cohort.

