Cohort 3. Our null hypothesis is that the additional homologous booster vaccine dosing with the BNT162b2 after prior BNT162b2 vaccination will increase mean titers in the spike IgG assay by at least 300%. Alternate hypothesis is that heterologous vaccination with the BNT162b2 after prior mRNA-1273 vaccination will increase mean titers by an additional 300%- that is to 600%. To achieve 80% power at a significance level alpha = 0.05, a one sided two sample t-test would require 22 samples per group to detect differences in mean titers of 750 AU/mL and 1500 AU/mL at an estimated standard deviation of 1000 AU/mL. Given we estimate 30-40% patients with have had prior mRNA-1273 vaccination and accounting for 5% dropout rate, we will thus use a planned sample size of 80.

Statistical analysis

To assess our goals as outlined above, statistical analysis will be done in the R software environment. The primary aim of cohorts 1 and 2 examining the seroconversion rates after 4 weeks will be checked with a one sample z test of proportions. The primary aim of cohort 3 examining the increase in mean Spike IgG titers will be checked with a one sided two sample t-test. Secondary aims involving the significance of associations between certain malignancies and the rates of seroconversion in our prospective single arm study will be measured by Fisher's exact and Cochran- Mantel-Haenszel tests depending on if analysis is conducted by a stratified variable (Cochran- Mantel-Haenszel) or not (Fisher's exact). The more complicated relationship between patients' seroconversion rates, their recent receipt of medical treatment, and additional factors such as history of malignancy will be examined through a multivariate logistic

regression model. After addressing the appropriateness of interaction terms, a Wald test will be used to consider the statistical significance of all included variables at the $p < 0.05$ level.

Duration

Our study will follow patients from Aug 1, 2021 through November 2023, which will allow for sufficient time to assess follow-up serologies after COVID-19 vaccination infection in patients with cancer (24 months follow up).

Matching

Cohort 1

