Patients would serve as their own control. Baseline seropositivity rate by definition is 0% for the cohort but anticipating natural and laboratory variation we have based on statistical null hypothesis around a 10% seropositivity rate at 4 weeks and anticipate that booster vaccination will increase this to higher than 30%.

Planned intervention

Cohort 1

The planned intervention is to administer a booster dose of the BNT162b2 (Pfizer/BioNTech) or mRNA-1273 (Moderna) vaccine to patients that meet FDA/CDC criteria of cancer on active therapy or patients that have received a stem cell transplantation or CAR-T cell therapy in the last 2 years or those that have a negative spike IgG after having = completed one of the FDA's Emergency Use Authorized vaccination series for COVID-19 (i.e. 2 doses of the mRNA-based mRNA-1273 (Moderna), BNT162b2 (Pfizer/BioNTech), or a single dose of the adenovirus-based Ad26.COV2.S (Johnson & Johnson) vaccine, following completion of their vaccination series.

Cohort 2

The planned intervention is to administer an additional booster dose of the BNT162b2 (Pfizer/BioNTech) or Ad26.COV2.S (Johnson & Johnson) vaccine to patients that meet eligibility criteria for cohort 2 in a 1:1 randomization fashion with negative spike antibody vs. low positive antibody level serving as a stratification factor to ensure controlling for key confounder.

Cohort 3

The planned intervention is to administer an additional booster dose of the BNT162b2 (Pfizer/BioNTech) vaccine to patients that meet eligibility criteria for cohort 3 in a prospective single arm fashion in patients that had a poor serological response after standard vaccine series (including a third dose).

Participant recruitment

The study will both utilize data from the electronic health record to identify patients meeting the above inclusion criteria and enroll them on to the study and accept patients self-referred or referred by their provider at Montefiore Medical Center or external institutions. A consenting visit will be scheduled with each prospective patient. Following a carefully conducted and documented informed consent process subjects who consent for study participation will then be screened. Patients who qualify for booster COVID-19 vaccination as per FDA/CDC guidance and study criteria will then participate in our study.

Data and Safety Monitoring Plan

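### Cohort 1's promise of 5% significance and 80% power in every subset above 26 does not hold throughout under any version of the one-sample z test; an exact test with stated sidedness and a restated minimum size would fix it

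*Combined protocol and SAP*

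**What the plan says.** The cohort 1 paragraph of the Sample size section describes a one-sample test of proportions. On the null it says: "Null hypothesis is a positivity rate of 10% to account for some test variability". It puts the alternative above 30%, and the cohort 1 paragraph under Matching repeats this: the investigators "anticipate that booster vaccination will increase this to higher than 30" percent. The opening hypothesis of the same Sample size paragraph has a different figure: "booster vaccine dosing will induce detectable immunity by the spike IgG assay in at least 20% of individuals".

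For the two preplanned subsets (the highly immune suppressed, and everyone else), the paragraph says that the design "will still retain 80% power and 5% significance in the secondary preplanned subset analyses as long as cohort sizes per subset are >26". It expects sizes close to that limit: "We anticipate cohort sizes of at least 26 per cohort based on the numbers of seronegative patients identified in our prior study".

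The Statistical analysis section names the test: "The primary aim of cohorts 1 and 2 examining the seroconversion rates after 4 weeks will be checked with a one sample z test". That sentence covers the primary aim. No other test of a seroconversion rate against 10% appears anywhere, so its use in the subsets is inferred. For cohort 1 the plan does not state sidedness, a continuity correction or a responder cut-off. Only cohort 3 is called one-sided.

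**The concern.** With 27 to 60 patients and a 10% null, about 3 to 6 positives are expected under the null. The binomial distribution is right-skewed there, and the normal cut-off often falls one patient too low. Seropositive counts are whole numbers, so true error and power also move in a sawtooth as the subset grows. A claim about every size above 26 therefore has to be checked at each size, and subset sizes are not fixed in advance.

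At stake is the error rate for concluding that a subset, such as the highly immune suppressed patients, responds above the 10% background.

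**Working it through.** **Inputs.** From the cohort 1 Sample size paragraph: null p0 = 0.10, alternative p1 = 0.30, alpha 0.05, power 0.80, subset size above 26, total up to 250. From Statistical analysis: one-sample z test. Assumptions: the z test applies to the subsets, and 27 to 125 (half of 250) is the working range of subset sizes. Sidedness and continuity correction are unstated, so all four combinations are shown.

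**The plan's own figure.** The normal-approximation sample size is n = [(z_alpha·√(p0·q0) + z_beta·√(p1·q1)) / (p1 − p0)]², where √(0.10×0.90) = 0.300 and √(0.30×0.70) = 0.458.

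- One-sided: [(1.645×0.300 + 0.842×0.458)/0.20]² = 19.3, so 20; with continuity correction, 25.
- Two-sided: [(1.960×0.300 + 0.842×0.458)/0.20]² = 23.7, so 24; with continuity correction, 29.
- Exact binomial, one-sided 5%: power first reaches 80% at n = 25.

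The stated 26 is within two patients of the 24 and 25 results. At n = 26 and 27 the one-sided z test and the exact test share a cut-off of 6 positives, with true error 4.0% and 4.7% and power 83.7% and 86.4%. The number reproduces.

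**The guarantee above 26.** The uncorrected one-sided z test rejects at c = floor(n·(0.10 + 1.645·√(0.09/n))) + 1 positives. True error is P(X ≥ c) for a binomial(n, 0.10), and power is the same tail at 0.30. At n = 32: 32×(0.10 + 1.645×0.0530) = 5.99, so c = 6. The error is P(X ≥ 6) = 9.4%, and an exact 5% test would need 7.

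| n | z cut-off | true error | power | exact one-sided cut-off | true error | power |
|---|---|---|---|---|---|---|
| 27 | 6 | 4.7% | 86.4% | 6 | 4.7% | 86.4% |
| 28 | 6 | 5.5% | 88.7% | 7 | 1.8% | 78.0% |
| 29 | 6 | 6.4% | 90.7% | 7 | 2.2% | 81.2% |
| 30 | 6 | 7.3% | 92.3% | 7 | 2.6% | 84.1% |
| 32 | 6 | 9.4% | 94.9% | 7 | 3.6% | 88.7% |

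**All four versions of the z test, n = 27 to 125 (99 sizes).**

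| Version | True error | Lowest power at 30% |
|---|---|---|
| One-sided, uncorrected | mean 5.9%; above 5% at 70 sizes; maximum 9.4% (n=32) | 86.4% (n=27) |
| One-sided, corrected | above 5% at 19 sizes; maximum 5.8% (n=50) | 81.2% (n=29) |
| Two-sided, uncorrected | total above 5% at 35 sizes, maximum 8.0% (n=35); upper tail above 5% at 2 sizes, maximum 5.5% | 81.2% (n=29) |
| Two-sided, corrected | always below 5% | 74.4% (n=27); also below 80% at n=28 and 32 |

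No version keeps both 5% error and 80% power at every size above 26.

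**Primary analysis.** Assuming 200 to 250 analysed, the uncorrected one-sided z test has a mean true error of 5.5% and a maximum of 6.7%.

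**Exact test.** Error is at most the nominal level by construction. With one-sided 0.05, power from n = 25 upward falls below 80% only at n = 28, so it holds throughout from 29. With 0.025 in the upper tail, power is below 80% at n = 30 to 32 (78.8% at 32) and holds throughout from 33 (81.8%).

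**If the target were 20%.** At n = 27 the one-sided z test would have about 46% power, and the exact one-sided test at n = 29 about 36%.

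**The case against.** The strongest reply is that nothing was miscalculated: 26 reproduces, and the rest is the discreteness of small samples around a normal-approximation planning number. The first half stands, and nobody should read this point as saying that 26 is wrong. The second half does not rescue the sentence, because the plan promises both properties at every size above 26.

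A reader might also infer that the plan's real error rate is 9.4%, nearly twice nominal. The documents do not support that. The figure needs a one-sided, uncorrected test at exactly 32 patients, and neither choice is stated. The average for that version is about 5.9%. For the uncorrected two-sided test, the 8.0% total includes 2.5 points from the lower tail; a false claim of response concerns only the upper tail, at most about 5.5%. That upper tail does exceed its nominal 2.5% at 81 of the 99 sizes.

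Another tempting reading is that power fails at n = 28. That shortfall belongs to the exact test, which the plan does not name; the one-sided uncorrected z test has 88.7% there.

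Nor do the documents make these subsets cohort 1's main secondary claim. Testing them against 10% is absent from its list of secondary outcomes, and the cohort is described as exploratory or pilot.

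Finally, the 10% null is already an allowance over a baseline of 0% by definition. If the true background were 5% or 8% (assumed values), the n = 32 cut-off would give false positives at 0.5% or 3.9%. This softens the practical consequence, but the stated 5% is a claim about the 10% null.

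**Conclusion.** The blanket statement is wrong as written. The excess in true error ranges from under one percentage point (one-sided, corrected, peak 5.8%) to 4.4 points at worst (one-sided, uncorrected, peak 9.4%). The one version that controls error falls to 74% power at the smallest size covered. The conclusion does not depend on sidedness or correction, since all four versions fail somewhere. It does rest on the z test being used in the subsets, which is inferred, and on the 30% alternative.

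It is a minor point: the analyses are secondary and exploratory, 26 is defensible, and the effect on the primary analysis is small. The unreconciled 20% and 30% targets in the same paragraph matter far more for power.

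**What to change.** First reconcile the 20% and 30% statements, since every minimum size depends on the target rate. Then:

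- State the sidedness of the cohort 1 tests.
- Name the exact binomial test for the two subsets and, for consistency, for the cohort 1 primary analysis.
- Replace the limit of 26 with the size from which 80% power holds throughout: 29 for a one-sided 0.05 test, or 33 with 0.025 in the upper tail. Both assume a 30% alternative and must be recomputed if the target changes.

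The cost is one test name, one statement of sidedness and one number. The exact test is slightly conservative at some sizes. No extra patients are needed provided the subsets reach the restated minimum; the plan anticipates only at least 26, so that expectation should be checked.

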Have received an FDA authorized booster dose of mRNA (BNT162b2 or mRNA 1273) vaccine at least 28 days before study enrollment

Exclusion Criteria

Patients who have had a serious adverse reaction to any prior COVID-19 vaccines resulting in emergency room visit or hospitalization, had events related to myocarditis, thrombosis and thrombocytopenia syndrome or anaphylaxis to any prior dose of the COVID-19 vaccines.

Patients who have had a documented COVID-19 infection in the 90 days prior to study enrollment

Outcomes

Primary outcome: Rates of seroconversion for SARS-CoV-2 spike antibody after 4 weeks following an additional booster dose of BNT162b2/AdCov2.S COVID vaccine in patients that had a poor serological response after standard vaccine series (allowing additional booster dose)

Secondary outcomes: Safety of booster dose of BNT162b2 and AdCov2.S vaccines, correlation between malignancy type and prior treatment type and seroconversion, correlation between timing of most recent cancer-directed treatment and seroconversion, correlation between the total number of cancer-directed treatments received and seroconversion, differences between booster efficacy dependent on prior vaccine type (BNT162b2 versus mRNA-1273), T cell responses at baseline and 4 weeks following vaccination, Antigen neutralization assay results at baseline and 4 weeks following vaccination, duration of sustained immunogenicity following vaccination in seropositive patients, correlations with baseline immune status correlates such as lymphocyte subsets/immune globulin levels

Safety monitoring.

Patients who have met all eligibility criteria will then be randomized 1:1 to receive either the BNT162b2 or AdCov2.S and then will be scheduled to receive their study dose at the Montefiore Vaccine Center. Each patient will be observed for a minimum of 15 minutes after their vaccination to monitor for any adverse

effects in the Montefiore Vaccine Center as per the Vaccine Center protocol.

Cohort 3

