On December 16, 2021 the CDC published updated recommendations regarding use of the Ad26.COV2.S (Johnson & Johnson) vaccine (<https://www.cdc.gov/media/releases/2021/s1216-covid-19-vaccines.html>) due to the rare but persistent adverse event thrombosis with thrombocytopenia syndrome (TTS) seen with the Ad26.COV2.S vaccine alone. They expressed a clinical preference for individuals to receive an mRNA COVID-19 vaccine over an Ad26.COV2.S vaccine, however, reaffirmed that receiving any vaccine is better than being unvaccinated. This recommendation, however, did not specify stipulations for our currently immunosuppressed patients with cancer population who have already received three prior mRNA COVID-19 vaccines with minimal or no response. Given our patient population remains at high-risk for severe COVID-19 despite three prior mRNA COVID-19 vaccines, we feel the administration and efficacy evaluation of Ad26.COV2.S (Johnson & Johnson) vaccine as a mix and match strategy for booster vaccination continues to remain warranted as part of our study. In fact, a recent study from South Africa does suggest excellent efficacy of a booster Ad26.COV2.S vaccine corroborating this approach¹⁵.

Some patients, however, remain hesitant to receive an Ad26.COV2.S given its rare but potentially severe adverse event as outlined above. Thereby, for study candidates who prefer not be randomized in cohort 2, participation in cohort 3 will be offered. Cohort 3 will be a prospective, non-randomized cohort to address the question of whether a switch mRNA vaccine approach might be more effective at achieving an increased immune response in poor responders to a prior series of three mRNA vaccinations (mRNA-1273 (Moderna) or BNT162b2 (Pfizer/BioNTech)). Eligible patients will be prospectively followed to receive a BNT162b2 vaccine as a fourth dose evaluating their increase in mean SARS-CoV-2 Spike IgG titers above a pre-established threshold by 4 weeks following vaccination as the primary endpoint with further secondary endpoints regarding safety, neutralization antibody and T cell assays and durability of response with assessments at 3, 6, 12 and 24 months. As it is anticipated that about 60-70% of study candidates will have previously received BNT162b2 and 30-40% mRNA-1273, this cohort will allow an assessment of a switch approach in a non-randomized single arm fashion.

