Our proposed study is a prospective single arm study, which will aim in an exploratory/pilot fashion to assess the following variables in a population of patients with cancer with prior vaccination against COVID-19.

- To study the difference in mean titers for SARS-CoV-2 spike IgG in patients with cancer after administering an additional (fourth) booster dose of the BNT162b2 vaccine in patients that had a poor serological response after standard homologous (BNT162b2 → BNT162b2) vs. heterologous (mRNA-1273 → BNT162b2) vaccine series (including a third dose).
- To study safety and side effects from an additional booster dose of the BNT162b2 COVID vaccine

Inclusion criteria:

Our target population consists of patients with a known or previous diagnosis of cancer who had received three prior doses of one of the mRNA based COVID-19 vaccines including a booster dose. Our study will employ the following inclusion criteria:

- Above the age of 18
- Have a diagnosis of prior or active malignancy- either hematological or solid tumor
- Have a negative or low-level SARS-CoV-2 spike IgG after at least 14 days of booster vaccination series irrespective of active/inactive cancer status, on observation, or active therapy.
- Have received an FDA authorized booster dose of mRNA (BNT162b2 or mRNA 1273) vaccine at least 28 days before study enrollment

- Decline to participate in cohort 2 requiring randomization of BNT162b2 and Ad26.CoV2.S vaccines

Exclusion Criteria

- Patients who have had a serious adverse reaction to any prior COVID-19 vaccines resulting in emergency room visit or hospitalization, had events related to myocarditis, thrombosis and thrombocytopenia syndrome or anaphylaxis to any prior dose of the COVID-19 vaccines.
- Patients who have had a documented COVID-19 infection in the 90 days prior to study enrollment

Outcomes

Primary outcome: To compare the increase in mean titers for SARS-CoV-2 spike antibody after 4 weeks following a homologous (BNT162b2 → BNT162b2) vs. heterologous (mRNA-1273 → BNT162b2) additional booster dose of COVID vaccine in patients that had a poor serological response after standard vaccine series (including a third dose).

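### Cohort 2 states its hypotheses as homologous versus heterologous boosting, but by the protocol's own Cohort 3 definition its BNT162b2 control arm is part heterologous

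*Combined protocol and SAP*

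**What the plan says.** All references are to the combined protocol and SAP.

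- **Sample size, Cohort 2.** The control hypothesis reads "Our null hypothesis is that the additional homologous booster vaccine dosing will induce detectable immunity", with the rate set "by the spike IgG assay in at least 25% of individuals". The alternative is that a heterologous dose of the adenoviral vaccine "will increase this seroconversion rate by an additional 25%- that is to 50" per cent. The size follows: "With an alpha of 0.05 and 80% power to detect the difference, we would require a sample size of 46 in each group".
- **Cohort 2, inclusion criteria.** Either mRNA product qualifies: "Have received an FDA authorized booster dose of mRNA (BNT162b2 or mRNA 1273) vaccine at least 28 days before study enrollment". All eligible patients are randomised 1:1 to BNT162b2 or Ad26.COV2.S, so every control receives BNT162b2 whatever they had before.
- **Cohort 3, aims.** The terms are defined by product: "standard homologous (BNT162b2 → BNT162b2) vs. heterologous (mRNA-1273 → BNT162b2) vaccine series". The Cohort 3 sample-size paragraph uses the same definition and hypothesises the larger titre rise after the switch (600% against 300%).
- **Cohort 3, rationale.** The expected mix is "about 60-70% of study candidates will have previously received BNT162b2 and 30-40% mRNA-1273".
- **Planned intervention, Cohort 2.** Randomisation is stratified on baseline antibody status only, "with negative spike antibody vs. low positive antibody level serving as a stratification factor". Prior mRNA product enters Cohort 2 only as a secondary outcome.

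**The concern.** Cohort 2 is the study's only randomised mix-and-match comparison. Its hypotheses are stated in terms of homologous and heterologous boosting, while its arms are defined by the product given on the study day. The two coincide only for patients previously given BNT162b2. For patients previously given mRNA-1273, both arms are a switch under the Cohort 3 definition.

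Two things are at stake. The first is interpretation: a difference between the arms would answer which product does better in this mixed population, not whether switching beats repeating. The second is power: if the 25% planning rate describes only BNT162b2-primed patients, and switching within mRNA products helps as Cohort 3 hypothesises, the control rate would exceed 25% and the planned 25-point difference would shrink.

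**Working it through.** **Inputs.** From the Cohort 2 sample-size paragraph: control 25%, Ad26.COV2.S 50%, alpha 0.05, 46 per arm. From the Cohort 3 rationale: share with prior mRNA-1273, f = 0.30 to 0.40; it is given for study candidates in general, so applying it to Cohort 2 is an assumption. The seroconversion rate r for BNT162b2 after mRNA-1273 is not in the documents. I vary it from 25% (no switch benefit) to 50% (equal to Ad26.COV2.S).

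**Step 1: reproduce the plan's figure.** Two proportions, pooled variance under the null, no continuity correction, one-sided 5%, with p̄ = (0.25 + 0.50)/2 = 0.375:

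n = [1.645·√(2·0.375·0.625) + 0.842·√(0.25·0.75 + 0.50·0.50)]² / 0.25² = (1.126 + 0.557)² / 0.0625 ≈ 45.3, rounded up to 46. Power at 46 is 80.5%.

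The stated size is matched on a one-sided basis; the same formula two-sided gives 58. The paragraph does not state sidedness. That is a separate point, and the one-sided basis is used below because it recovers the plan's own number.

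**Step 2: composition of the control arm.** Switched patients among 46 controls: 0.30 × 46 = 13.8 to 0.40 × 46 = 18.4, so about 14 to 18.

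**Step 3: control rate if the 25% describes BNT162b2-primed patients only.** Control rate p_c = 0.25·(1 − f) + r·f. Power = Φ{[(0.50 − p_c)·√46 − 1.645·√(2p̄(1 − p̄))] / √(p_c(1 − p_c) + 0.25)}, with p̄ = (p_c + 0.50)/2.

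Example, f = 0.40 and r = 0.50: p_c = 0.35, difference 0.15, p̄ = 0.425. The numerator is 0.15 × 6.782 − 1.645 × 0.699 = −0.133 and the denominator is 0.691, so power = Φ(−0.192) = 42.4%.

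| Assumed switch rate r | Control rate (f = 30% to 40%) | Difference, points | Power at 46 per arm | n per arm for 80% |
|---|---|---|---|---|
| 25% | 25.0% | 25.0 | 80.5% | 46 |
| 30% | 26.5 to 27.0% | 23.5 to 23.0 | 75.6 to 73.9% | 52 to 55 |
| 35% | 28.0 to 29.0% | 22.0 to 21.0 | 70.3 to 66.5% | 60 to 66 |
| 40% | 29.5 to 31.0% | 20.5 to 19.0 | 64.5 to 58.5% | 70 to 82 |
| 50% | 32.5 to 35.0% | 17.5 to 15.0 | 52.4 to 42.4% | 97 to 134 |

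**Step 4: the subgroup in which the labels do hold.** BNT162b2-primed patients among 46 per arm: 0.60 × 46 = 27.6 to 0.70 × 46 = 32.2, taken as 27 to 32. At 25% versus 50%, one-sided 5%, power is 60.3% to 66.8%.

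**The case against.** The strongest reply is that the design is already stated by product. The Cohort 2 rationale, first aim, primary outcome and planned intervention all name BNT162b2 and Ad26.COV2.S; for Cohort 2 the words homologous and heterologous occur only in the sample-size paragraph. That is correct, and it means the repair is mainly to that paragraph. It remains the place where the hypotheses are stated.

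A second reply is that homologous may mean same platform there (mRNA after mRNA), or that the 25% was meant for the whole BNT162b2 arm. Either reading leaves 46 per arm intact, and the documents do not rule them out. But the next paragraph, for Cohort 3, applies the same term to BNT162b2 after BNT162b2, so a change of meaning needs to be written down.

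A third reply is that stratifying on prior product is a preference: chance imbalance in an unstratified factor is covered by the test's error rate, efficacy by prior vaccine type is already a secondary outcome, and the cohort is described as exploratory. This stands against calling the omission an error, and it tempers the severity. It does not make the stated hypothesis match the arms.

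Two stronger readings are tempting, and the documents do not support them. A reader might infer that the randomised difference is biased toward zero. It is not: prior product is a baseline characteristic with the same expected mix in both arms, so the product comparison is unbiased for the patients enrolled. A reader might also infer that Ad26.COV2.S-primed patients could enter Cohort 2, because the listed criteria do not ask for a same-product series. The target-population sentence, the Cohort 2 rationale and the Cohort 3 background all describe patients with prior mRNA series, so this does not hold up.

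**Conclusion.** The mismatch between the stated Cohort 2 hypotheses and its arms is real and can be checked from the text. Under the protocol's product-level definition, about 14 to 18 of 46 controls would receive a heterologous dose, assuming the 30-40% candidate mix carries over. The comparison of Ad26.COV2.S with BNT162b2 stands; the heterologous-versus-homologous reading of it does not.

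The power loss is conditional. It requires both that the 25% refers to BNT162b2-primed patients and that switched patients exceed 25%. Cohort 3 hypothesises a benefit in that direction, but for mean titre, not for the proportion above 1000 AU/ml, so it supplies no rate. Loss therefore ranges from none to roughly half of the stated power across the assumed rates. This should be fixed, but it does not threaten the validity of the randomised comparison.

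**What to change.** 1. Reword the Cohort 2 hypotheses in the sample-size section as Ad26.COV2.S versus BNT162b2, and state which patients the 25% describes: the whole BNT162b2 arm or only those previously given BNT162b2. If the latter, give an assumed rate for switched patients and recompute the size.
2. Include prior mRNA product, together with baseline antibody status, as a stratum or covariate in the between-arm primary comparison. Add it as a randomisation stratum if allocation has not started. The statistical analysis section currently assigns Cohort 2 a one-sample z test, so a between-arm test has to be written in any case.
3. Confine any homologous-versus-heterologous statement to a prespecified BNT162b2-primed subgroup, and declare in advance that it holds only about 27 to 32 patients per arm, with roughly 60-67% power at 25% versus 50%.

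Items 1 and 2 cost wording and one analysis factor; COVID vaccine history is already collected at screening. Item 3 costs precision. Restoring 46 BNT162b2-primed patients per arm would need 46/0.7 to 46/0.6, about 66 to 77 per arm before dropout, or 132 to 154 in total against the planned maximum of 100. Declaring the limitation is the cheaper course.

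### Cohort 2's 46 per group matches the stated alpha and 80% power only under a one-sided two-sample test, and the plan states no sidedness for this cohort

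*Combined protocol and SAP*

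**What the plan says.** The Cohort 2 paragraph of Sample size puts seroconversion with a further BNT162b2 dose at 25% ("by the spike IgG assay in at least 25% of individuals") and says that Ad26.COV2.S "will increase this seroconversion rate by an additional 25%- that is to 50"%. It continues: "With an alpha of 0.05 and 80% power to detect the difference, we would require a sample size of 46 in each group". The total follows from that: "Accounting for 5% dropout rate, we will thus use a planned sample size of up to 100 subjects". Under Safety monitoring for Cohort 2, patients are "randomized 1:1 to receive either the BNT162b2 or AdCov2.S".

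Statistical analysis gives Cohorts 1 and 2 a one-sample z test of proportions for the primary aim, again without sidedness.

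Cohort 3 is treated differently. Its sample size paragraph says that "a one sided two sample t-test would require 22 samples per group", and Statistical analysis repeats that its test is one-sided. These are the only two places where the plan declares the sidedness of a test.

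**The concern.** When alpha of 0.05 is given without qualification for a randomised comparison, many readers take it as two-sided. On that reading 46 per group does not give the stated power. The contrast with Cohort 3, where the one-sided choice is written out, encourages it.

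Cohort 2 is the only randomised comparison in the study, so its decision rule should be unambiguous. With sidedness open, a result favouring Ad26.COV2.S with a two-sided p-value between 0.05 and 0.10 would be positive under one reading and negative under the other, and the choice could be made after the data are seen. The chance of a false claim in favour of Ad26.COV2.S is 5% under a one-sided test and 2.5% under a two-sided one.

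**Working it through.** **Inputs (Sample size, Cohort 2).** p1 = 0.25, p2 = 0.50, difference 0.25, alpha 0.05, power 80% (z = 0.8416), equal allocation. The mean rate is 0.375.

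**Sample size per group, two-sample z test with pooled variance under the null:**

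n = [z_a × √(2 × 0.375 × 0.625) + 0.8416 × √(0.25 × 0.75 + 0.50 × 0.50)]² / 0.25²

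The square roots are √0.46875 = 0.6847 and √0.4375 = 0.6614.

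- One-sided, z_a = 1.645: (1.1262 + 0.5567)² / 0.0625 = 2.832 / 0.0625 = 45.3, so **46**. This is the plan's figure.
- Two-sided, z_a = 1.960: (1.3419 + 0.5567)² / 0.0625 = 3.605 / 0.0625 = 57.7, so **58**.

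**Other two-sample formulas (n per group, rounded up):**

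| Formula | One-sided 0.05 | Two-sided 0.05 |
|---|---|---|
| Pooled z | 46 | 58 |
| Arcsine | 46 | 58 |
| Unpooled z | 44 | 55 |
| Continuity-corrected | 54 | 66 |

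No two-sided version comes near 46.

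**Dropout.** 2 × 46 = 92, and 92 / 0.95 = 96.8, so 97. This fits a ceiling of 100, or 50 per group if every patient is evaluable.

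**Power, pooled z test.** Power = Φ[(0.25 × √n − z_a × 0.6847) / 0.6614].

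- Two-sided, n = 46: (1.6956 − 1.3419) / 0.6614 = 0.535, power 70.4%.
- Two-sided, n = 50: (1.7678 − 1.3419) / 0.6614 = 0.644, power 74.0%.
- One-sided, n = 46: (1.6956 − 1.1262) / 0.6614 = 0.861, power 80.5%.
- One-sided, n = 50: (1.7678 − 1.1262) / 0.6614 = 0.970, power 83.4%.

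**Check by full enumeration of the two binomials:**

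| Test | 46 per group | 50 per group |
|---|---|---|
| Pooled z, one-sided | 81.5% | 84.0% |
| Pooled z, two-sided | 69.9% | 74.5% |
| Fisher's exact, one-sided | 75.1% | 77.9% |
| Fisher's exact, two-sided | 62.5% | 67.5% |

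**Does the named one-sample test explain 46?** For one group against a fixed 25%, n = [(z_a × √0.1875 + 0.8416 × √0.25) / 0.25]². This gives 20.5 (so 21) one-sided and 25.8 (so 26) two-sided. At 46 patients its power would be 97.5% or 95.5%. It does not produce 46 under either reading.

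**Cohort 3 for comparison.** With a difference of 750 and SD of 1000, the normal approximation gives 2 × (1.645 + 0.8416)² × (1000/750)² = 22.0, so 22, one-sided. Two-sided it gives 28. The plan's 22 agrees with the sidedness that it declares there.

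**The case against.** The best defence is that the number is right and only a word is missing. Forty-six is what a one-sided 0.05 two-sample z test needs. The Cohort 2 alternative is worded as an increase, and the only sidedness declared anywhere in the plan is one-sided. Cohort 1's alternative is directional too and also lacks the label, so silence in this document is weak evidence of a two-sided intention. The cohort is also described as exploratory or pilot.

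Most of this stands. It rules out two stronger conclusions that a reader might draw:

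- *That the sample size was miscalculated or the cohort is underpowered.* The documents never say that Cohort 2 will be tested two-sided. If the test is one-sided, as the figure implies, the design has its stated power.
- *That 70% to 74% is the power of the planned analysis.* That range belongs to a two-sided two-sample z test, which the plan does not name.

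The defence does not supply the missing declaration. Directional wording describes the effect that is hoped for and does not define a rejection region. Cohort 3's alternative is equally directional, yet there the one-sided test was written out. An exploratory label does not remove the need for a stated alpha, power and sample size to be reproducible from the text.

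**Conclusion.** The point holds as an undeclared design choice, not as an arithmetic error. Among the usual two-sample calculations, 46 per group for 25% against 50% at 80% power is reproduced only with one-sided alpha of 0.05. Under two-sided 0.05 the requirement is 58 per group. Power is then about 70% at 46 and 74% at 50, so it stays below 80% even if all 100 patients are evaluable. At the design effect, the chance of missing the difference would be about 26% to 30% instead of 20%.

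These figures assume true rates of 25% and 50%, equal groups and a pooled two-sample z test. The shortfall is conditional on a two-sided test. What is not conditional is that the plan leaves the sidedness open, and that the one-sample test it names neither compares the randomised arms nor accounts for 46. This should be fixed, but it does not call the size of the cohort into question.

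**What to change.** 1. In Statistical analysis, replace the one-sample z test for Cohort 2 with a named two-sample comparison of proportions between the randomised arms, and state its sidedness. Adding a sidedness to the one-sample test would not resolve the point.
2. In Sample size, Cohort 2, take one of two routes:
   - state one-sided alpha of 0.05 with a justification, keeping 46 per group and about 80% power; or
   - keep two-sided 0.05 and restate the power as about 70% at 46 per group and 74% at 50.
3. Settle the choice before outcome data are seen. If data already exist, say so and disclose when and why the choice was made.

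The power figures in step 2 are for the pooled z test. If Fisher's exact test is named instead, quote its lower values.

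The cost is a sentence or two in each section and no extra patients. The stated power becomes less favourable if two-sided testing is kept.
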